11. PHOSPHORYLATION OF ERK ENDPOINT ANALYSIS

The primary objective of this trial is to evaluate the percentage reduction of p-ERK score from baseline and characterize safety and efficacy of different treatment sequence with the p-ERK score changes. The primary end point will be analyzed with a descriptive intent only. Hence no hypothesis testing will be performed. The Biomarker Population will be used for the reporting and the analysis of the primary endpoint, and all members of the biomarker population will have a positive BRAF V600E/K mutation.

We also will conduct an exploratory sensitivity analysis among all subjects with BRAF V600E mutation based on central lab testing for primary P-ERK Biomarker Analyses listed in Section 11.2.1. A summary will be created that lists the samples obtained for Immunohistochemistry Analysis. The lists of displays for P-ERK, including population to use for each display, are shown in Section 18.1.5 of the RAP.

11.1. Interim Analysis

No formal interim analysis will be conducted in this study.

11.2. Investigator Assessment of H-Score

The primary endpoint analysis will be the evaluation of the percentage change of the mean Phosphorylated Extracellular Signal-regulated Kinase (p-ERK) H-Score from baseline. At the beginning of IP treatment, the p-ERK H-Score will be determined for all participants in the biomarker population.

Change in biomarker status is most prominent within two weeks of start of treatment. Patients from arm A and arm B will be given combination therapy starting from week 9 after completion of 8 weeks of monotherapy. Therefore, changes in biomarker between screening and week 2 as well as between week 8 and week 10 will be summarized and listed. All visits for biomarker samples have a window of ± 7 days.

More specifically, the procedure for calculating the p-ERK score is shown below:

- Intra-tumoral expression levels of ERK, a tumor tissue biomarker, will be measured using immunohistochemistry methods that incorporated both intensity and distribution of staining. A value designated the H-Score will be derived by summing the percentages of cells staining at each intensity multiplied by the weighted intensity of staining (0, 1+, 2+, 3+: 3+ indicates the strongest staining, 2+ indicates medium staining, 1+ indicates weak staining, and 0 indicates no staining). H-Scores range from a minimum score of 0 to a maximum score of 300; the maximum score indicates the strongest expression. We will also collect a summary staining score for the tumor tissue which has potential values of 0 (no staining), 1+ (weak staining), 2+ (medium staining), and 3+ (strong staining).

$$\begin{aligned}
 H - Score &= (3 * \% \text{ Cells with strongest staining}) \\
 &\quad + (2 * \% \text{ Cells with medium staining}) \\
 &\quad + (1 * \% \text{ Cells with weak staining}) \\
 &\quad + (0 * \% \text{ Cells with no staining}) \uparrow
 \end{aligned}$$

All p-ERK H-Score data will be recorded on the eCRF, including data on % positivity for all participants in the biomarker population, which is calculated using the equation below:

$$\begin{aligned}
 \% \text{ Positivity} &= \% \text{ of cells with weak staining} \\
 &\quad + \% \text{ of cells with medium staining} \\
 &\quad + \% \text{ of cells with strong staining} \uparrow
 \end{aligned}$$

Summary statistics, graphics, and statistical modeling will be conducted on the biomarker population for each arm of the study.

11.2.1. Primary p-ERK Biomarker Analyses:

Analyses from this section will utilize p-ERK H-scores from pre-dose, 2-week, 8-week, and 10-week biopsies. Summary statistics (mean, standard deviation, median, minimum, and maximum) will be reported at each time point and for change (actual and percent

changes) from baseline to two weeks in Arm C and for change from 8-week and 10-week in Arms A and B for p-ERK using H-score values.

Depending upon data availability, \log_2 -transformed values of p-ERK H-Score results will be analyzed by analysis of variance (ANOVA) for each cohort. In some cases, it is possible for p-ERK H-Scores to have a value of zero, and if these zero H-Scores are present in the data, we will add an offset of one to all values before conducting any \log_2 -transformations. This analysis will consider time and treatment as the fixed effect, and subject as a random effect. The H-Score calculation at either screening (analysis for combo arm) or week 8 (analysis from monotherapy arms) is the test comparison and the H-Score calculation at either week 2 (analysis for combo arm) or week 10 (analysis from monotherapy arms) is the reference calculation. The analysis will be performed using the mixed linear models procedure within the SAS/STAT module of the SAS system. Point and $(1-2\alpha^*)$ interval estimates of the difference in least-square (LS) means of the test less the reference treatment will be derived using SAS code such as that described below:

```
proc mixed;  
class trt time subject;  
model HScore = time trt;  
random subject;  
lsmeans trt;  
estimate 'B vs. A' trt -1 1 / cl alpha=0.05  
run;
```

(In this code, trt, HScore, and time refer to treatment given, H-Score Value, and the time of H-Score analysis, respectively).

For each primary endpoint, results from these analyses will be exponentiated to obtain point and 90% confidence interval estimates of the appropriate test to reference ratios of geometric least-squares (GLS) means.

Assumptions underlying these analyses will be assessed. If the assumptions are seriously violated, then nonparametric methods will be considered.

The mean and median Intra-tumoral expression levels of ERK over time will be plotted, with treatment highlighted using appropriate graphical techniques (e.g. trellis, plotting symbol, and colour).

For further exploratory purposes and if data warrant, multivariate proportional Cox models examining the relationships between PFS and DoR and decreases in H-Score from none or mono therapy to combo therapy may be examined with age, sex, ECOG status, initial drug exposure (combo therapy vs. monotherapy), and BRAF mutation type (V600E vs. V600K) as potential covariates using backward selection. If multivariate proportional Cox models are developed, a listing containing the values for each variable as part of the Cox model will be created.

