## STUDY DESIGN

Figure 1 Study Schema

This is a three-arm, open label, randomised, Phase II study comparing the upfront combination of dabrafenib (GSK2118436) with trametinib (GSK1120212) versus the combination after eight weeks of monotherapy treatment with dabrafenib or trametinib.

Approximately 54 eligible patients with histologically confirmed cutaneous melanoma that is either metastatic or unresectable (stage IIIc or IV) and BRAF V600E/K mutation positive as determined by a local laboratory will be randomised, 1:1:1 to one of the three treatment arms.

- Arm A: dabrafenib 150mg BID continuously during eight weeks followed by the combination of trametinib 2mg once daily with dabrafenib 150mg BID until disease progression, death or unacceptable toxicity.
- Arm B: trametinib 2mg/day continuously during eight weeks followed by the combination of trametinib 2mg once daily with dabrafenib 150mg BID until disease progression, death or unacceptable toxicity.
- Arm C: trametinib 2mg/day plus dabrafenib 150mg BID continuously until disease progression, death or unacceptable toxicity.

Monitoring will be performed throughout the study according to the Time and Events Table (Table 19). Protocol specified guidelines for dose adjustments, interruptions and discontinuation due to AEs/liver toxicity are provided in Section 5.8, and Section 5.9, respectively. The visits allow a window of +/- 7 days. Dose interruptions should not alter the assessment schedule for any subsequent treatment period.

Biomarker analysis will be performed on blood, tumour and skin samples according to the Time and Events Table (Table 19).

Clinical responses will be evaluated using RECIST 1.1 criteria every 8 weeks. The response evaluation may be performed earlier if clinically indicated (for example, if patient has symptomatic deterioration suggesting rapid disease progression or to confirm clinical response at 4 weeks after achieving response).

Patients who show either radiographic or clinical progression of disease according to the investigator during the monotherapy treatment period in arm A or B will be able to go on to the combination treatment before completion of the 8 weeks monotherapy treatment. Patients will be treated with the combination treatment until disease progression, unacceptable toxicity or withdrawal from study whichever comes first.

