- 5. Baseline MRI (preferred) or CT (only if MRI contraindicated or unavailable) of the brain must be performed on all patients to rule out current leptomeningeal metastases, brain metastases, or spinal cord compression secondary to metastasis. Post-baseline scans should be performed in all patients with documented metastases at baseline and as clinically indicated (e.g., symptoms suggestive of CNS progression) in all patients.
- 6. Lesion assessments must be done for chest, abdomen, pelvis, and any area of known disease. Lesion assessment by contrast CT (preferred) or MRI must be performed within 5 weeks prior to randomisation and at the times indicated until disease progression, death, or withdrawal of consent, whichever occurs first. (See Section 7.3.3 for instructions regarding chest X-Rays and CT assessment.) Target and non-target lesions must be identified at the time of screening and the same lesions must be re-assessed at each timepoint in a consistent manner according to RECIST, version 1.1. The same diagnostic method, including use of contrast when applicable, must be used throughout the study to evaluate each lesion. Lesion measurements will be taken using ruler or calipers. The Week 8 assessment for patients in arms A & B should be done before starting the combination treatment. If the last assessment was > 8 weeks prior to study withdrawal and disease progression had not been documented, a disease assessment should be obtained.

- 7. Randomisation will occur via RAMOS on Day 1.
- 8. Refer to Section 7.4.6 for details regarding vital sign measurements.
- 9. A complete physical examination will be performed at Screening and End-of-study; brief physical examinations will be performed at all other timepoints as indicated. In females, genitourinary exam should include a visual inspection of the cervix. If the patient has had a genitourinary and rectal exam within 6 months of screening the genitourinary and rectal exam do not need to be repeated. Refer to Section 7.4.7 for details.
- 10. An ophthalmic examination will be performed at Screening; additional ophthalmic examinations will be performed only as symptomatically warranted. Refer to Section 7.4.5 for details.

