9.2.9. Multiple Assessments

All data will be reported according to the nominal visit date for which it was reported (that is, no visit windows will be applied during dataset creation). Unscheduled data is included only in summary sections and in shift summaries of laboratory (e.g., vital signs/ECG) data labelled worst- case. For summaries that collapse data across multiple planned time intervals, select the worst-case data at each collapsed interval.

If multiple assessments on different days are reported for the same scheduled assessment, then the latest assessment for that scheduled assessment will be analyzed.

If multiple assessments are reported on the same date for the same scheduled planned time, then the worst-case result will be analyzed, with the exception of laboratory data reported from both central and local laboratories. If laboratory data is reported from both central and local laboratories with the same date, then the central laboratory data will be analyzed to provide consistency with measurements from other subjects. For example, for ECG data where 3 assessments are collected for each scheduled planned time, the first 3 measures will be used to compute the mean values for ECG intervals at each scheduled planned time.

Data from all assessments (scheduled and unscheduled), including multiple assessments, will be included in listings.

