Treatment Arm	Comparison	N	LS Mean Num.	LS Mean Demon.	Ratio Estimate	Lower 90% Confidence Limit	Upper 90% Confidence Limit
GSK2118436 BID 8W then GSK1120212 QD + GSK2118436 BID	B vs A						
GSK1120212 QD 8W then GSK1120212 QD + GSK2118436 BID	B vs A						
GSK1120212 QD + GSK2118436 BID	B vs A						

Comparison for H-Score Times: B = Combo Therapy and A = Monotherapy or No Therapy (for Cohort that has Combination Therapy at start of study)

Example HScore5
Protocol: IMM123456
Population: Safety

Page 1 of x

Table X
Multivariate Proportional Cox Model Examining the relationship between
H-Score and Progression Free Survival/Duration of Response

Parameter	Parameter Estimate	P-Value	HR	Low 95% CI	High 95% CI
Decrease in H-Score (Log 2 Scale)					
Age					
Sex					
ECOG Status					
Initial Combo therapy					
V600E Status					

Example HScore6
 Protocol: BRF116613
 Population: Biomarker

Table X
 Correlation of Changes in H-Score after Two Weeks of Combo Therapy and Changes in Tumor Burden

Clinical Marker of Interest	Treatment Arm	Spearman's Coefficient	N
% Change in Sum of Lesion Diameters	GSK2118436 BID 8W then GSK1120212 QD + GSK2118436 BID		
% Change in Sum of Lesion Diameters	GSK1120212 QD 8W then GSK1120212 QD + GSK2118436 BID		
% Change in Sum of Lesion Diameters	GSK1120212 QD + GSK2118436 BID		

Example HScore7
 Protocol: XYZ100001
 Population: Intent-to-Treat/Safety/Other study specific

Table X
 Summary of Investigator/Independent Reviewer/etc.-Assessed Best Response (without or with confirmation)
per baseline H-Score Category (RECIST 1.1 Criteria)

	Treatment A (N=300)	Treatment B (N=200)	Treatment C (N=200)	Total (N = 54)
p-ERK IHC H-Score btw. 200-300				
Complete Response	22 (7%)	10 (5%)	10 (5%)	
Partial Response	30 (10%)	40 (20%)	50 (25%)	
Stable Disease	153 (50%)	110 (55%)	100 (50%)	
Non-CR/Non-PD	3 (1%)	0	0	
Progressive Disease	70 (23%)	33 (17%)	33 (17%)	
Not Evaluable	25 (9%)	7 (3%)	7 (3%)	

Response Rate

CONFIDENTIAL

BRF116613

CR+PR	52 (17.3%)	50 (25.0%)	60 (30.0%)
95% Confidence Interval	(13.2%, 22.1%)	(19.2%, 31.6%)	(23.7%, 36.9%)
p-ERK IHC H-Score btw. 100-200			
Complete Response	22 (7%)	10 (5%)	10 (5%)
Partial Response	30 (10%)	40 (20%)	50 (25%)
Stable Disease	153 (50%)	110 (55%)	100 (50%)
Non-CR/Non-PD	3 (1%)	0	0
Progressive Disease	70 (23%)	33 (17%)	33 (17%)
Not Evaluable	25 (9%)	7 (3%)	7 (3%)
Response Rate			
CR+PR	52 (17.3%)	50 (25.0%)	60 (30.0%)
95% Confidence Interval	(13.2%, 22.1%)	(19.2%, 31.6%)	(23.7%, 36.9%)

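### SAP 11.2.1 treats every nominal Week 8 biopsy in Arms A and B as monotherapy, although some may follow the switch to the combination

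*SAP*

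**What the plan says.** **The contrast.** SAP 11.2.1, the section on primary p-ERK analyses, reports summary statistics "for change from 8-week and 10-week in Arms A and B for p-ERK using H-score values". It also fits a mixed model in which the two samples compared in the monotherapy arms are identified by week. Mock-up HScore4 in SAP 18.2.3 labels the two sides "B = Combo Therapy and A = Monotherapy or No Therapy".

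**When the combination starts.** SAP 11.2 states: "Patients from arm A and arm B will be given combination therapy starting from week 9 after completion of 8 weeks of monotherapy". Protocol 3 and SAP 3 add an exception: Arm A or B patients with radiographic or clinical progression "will be able to go on to the combination treatment before completion of the 8 weeks monotherapy treatment".

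**When samples are taken and how they are assigned.** SAP 11.2: "All visits for biomarker samples have a window of ± 7 days". SAP 9.2.9: "All data will be reported according to the nominal visit date for which it was reported", with no analysis windows. If one scheduled assessment has results on several days, "then the latest assessment for that scheduled assessment will be analyzed". Table 19 footnote 1 keeps all assessments on the calendar.

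**The only ordering rule.** Table 19 footnote 6, attached to the lesion assessment row: "The Week 8 assessment for patients in arms A & B should be done before starting the combination treatment". The biopsy rows carry footnotes 21 and 22, and neither orders the Week 8 biopsy relative to the first combination dose.

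**The concern.** The Week 8 to Week 10 change in Arms A and B is meant to show what the second drug does to p-ERK after eight weeks of one drug. It does so only if the Week 8 sample was taken on one drug. The plan assumes this from the visit name, yet permits cases where it is untrue.

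A mislabelled pair does not drop out. It enters Table 5.0030 (change from Week 8 to Week 10), Table 5.0040 (mixed model), their V600E counterparts 5.0070 and 5.0080, the correlation with tumour burden in Table 5.0100, and the optional Cox models. The p-ERK listing mock-up (HScore10) shows planned time and study day but no combination start date, so a reader of the report could not pick these pairs out. With 15 evaluable patients per arm, each such pair is 1/15 = 6.7% of the arm. The study is descriptive, so the estimate is itself the result.

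**Working it through.** **1. The plan's own figures.** Precision: t(0.975, 14 df) × SD / √15 with SD 30 gives 16.613, against the stated 16.61. All five rows of the SD table reproduce. Power for an 80% reduction with SD 70, n = 15 and a two-sided paired t-test is 98.4%, against the stated >97%. Both concern baseline to Week 2. That comparison does not use the Week 8 sample, so nothing below changes them.

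**2. Early switch.** Take a patient who progresses and switches at Week 6. Assessments stay on the calendar, so the biopsies at Weeks 8 and 10 fall after two and four weeks of combination. Both are combination samples; SAP 11.2.1 and HScore4 count the first as monotherapy. This follows from the text alone and needs no assumption about windows.

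**3. Late-window biopsy.** Counting weeks as multiples of seven days, Week 8 is Day 56 with window 49–63, and Week 10 is Day 70 with window 63–77. The windows meet at Day 63, so the nominal two-week interval can run from 0 to 28 days. If the combination starts on Day 57 and the biopsy is taken late but within window, the Week 8 sample follows up to about a week of combination. That requires the biopsy to be separated from the visit at which the combination begins. Footnote 22 lets a dermatologist, surgeon or radiology-qualified physician take it, so a separate appointment is plausible, but the documents give no frequency.

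**4. Effect on the estimate.** Let f be the fraction of Arm A/B pairs whose Week 8 sample already has the full combination effect, and so shows no further change. Then:

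- arithmetic mean change = (1 − f) × true mean change;
- log ratio = (1 − f) × true log ratio, so the geometric mean ratio becomes (true ratio)^(1 − f).

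The documents give no Week 8 to Week 10 effect. The 80% reduction from the Week 2 power statement is borrowed for illustration, and f is assumed:

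| f | Mean reduction (true 80) | Geometric mean ratio (true 0.20) | Reduction implied by the ratio |
|---|---|---|---|
| 0.10 | 72 | 0.235 | 76.5% |
| 0.20 | 64 | 0.276 | 72.4% |
| 0.30 | 56 | 0.324 | 67.6% |

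On the ratio scale the loss in apparent reduction is smaller than the factor (1 − f) suggests.

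**5. How large might f be?** The protocol background cites median PFS of 5.1 months for dabrafenib and 4.8 months for trametinib. With a constant hazard, the proportion with an event by 56 days (56/30.4375 = 1.84 months) is 1 − 0.5^(1.84/5.1) = 22% and 1 − 0.5^(1.84/4.8) = 23%. This is an upper guide to early switching, not an estimate: the first scheduled scan is at Week 8, so an earlier switch needs clinical or unscheduled radiographic progression.

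**6. Price of restricting the contrast.** With SD 30, again borrowed, the 95% half-width is 18.13 with 13 pairs, 19.06 with 12 and 21.46 with 10, against 16.61 with 15.

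**The case against.** The strongest reply is that the planned path largely protects itself. Medication is dispensed at the four-weekly visits, which share the ±7-day window, so the second drug would naturally be handed out at the Week 8 visit. If that visit slips, so does the switch. A reader might infer from the dates in step 3 that 7 of the 15 permitted Week 8 days (57–63) are contaminated. The documents do not support that: no section fixes the switch at Day 57 regardless of the visit, and a count of permitted days is not a probability. This stands, and leaves the window route possible but unquantified.

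Second, the SAS note in SAP 11.2.1 describes the treatment variable as treatment given, and HScore4 labels the comparison by therapy. The programmer might therefore intend actual treatment. But the accompanying text fixes the two samples by week, and actual treatment in SAP 9.2.10 is an arm-level variable for the whole treatment period. The SAP is ambiguous here, and the ambiguity is what needs resolving.

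Third, a reader might infer that the estimate is always pulled towards zero. Attenuation is the expected direction for late-window samples, since the SAP itself expects the largest change within two weeks of starting treatment. Early switchers are progressing. Their p-ERK on monotherapy, and its course on the combination, may differ from other patients', so the direction for them is uncertain.

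Fourth, a reader might infer that the study's sizing or its whole primary endpoint fails. It does not: the endpoint is defined as change from baseline, precision and power rest on baseline to Week 2, and no hypothesis is tested. That lowers the severity but does not make a mislabelled summary correct.

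**Conclusion.** The point holds as a labelling gap in the Arm A/B Week 8 to Week 10 analysis. The current text permits post-switch Week 8 biopsies, and no stated rule identifies, reclassifies or separates them. The early-switch route follows directly from the design; the late-window route is possible but depends on how visits run.

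The size is unknown. The (1 − f) relation assumes that affected pairs already carry the full effect and that the remaining pairs share the true one. The values of f and the 80% effect are illustrations, and a sample taken within a week of the switch may carry only part of the effect. Baseline-to-Week 2 results and sizing are unaffected. This should be fixed before the analysis is run, but it does not undermine the trial.

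**What to change.** 1. In SAP 11.2 and 11.2.1, classify each Arm A/B biopsy by the treatment actually being taken on the biopsy date. Protocol 5.7 already has treatment start and stop dates recorded.
2. Base the monotherapy-to-combination contrast on Week 8/Week 10 pairs whose Week 8 sample precedes the first combination dose. Count post-switch Week 8 samples by arm and report them separately.
3. Keep the nominal-visit analysis over all pairs as a sensitivity summary. Excluding early switchers selects on progression after randomisation, so the restricted result should not stand alone.
4. Do not replace the pair with a biopsy about two weeks after an early switch. None is scheduled: biopsies fall on Day 1, at Weeks 2, 8 and 10, and at progression.
5. Add the combination start date to the p-ERK listing.
6. Extend Table 19 footnote 6 to the Week 8 biopsy for patients who complete the monotherapy period. The treatment-switching rule is untouched.

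The cost is programming on data already collected, one listing column and one footnote. The downside is that a few pairs leave the main Week 8 to Week 10 summary, with the loss of precision shown in step 6 of the working.

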# 9.2. Study Design Considerations

#### 9.2.1. Sample Size Assumptions

Based on feasibility a sample size of 54 patients will be enrolled in this trial in 1:1:1 ratio to one of the three treatment arms allowing a total of 20% early dropout rate. Assuming as large as 30% standard deviation (s.d.) of percentage reduction of pERK score from baseline, 15 patients per treatment arm will be sufficient to ensure that the 95% confidence interval (CI) will be the mean  $\pm 16.61\%$ . With 15 patients per treatment arm, the study will have >97% power to detect 80% reduction of pERK score from baseline to Week 2 within a treatment group (with s.d.=70%, alpha=0.05, two sided paired t-test).

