5. SAMPLE SIZE CONSIDERATIONS

5.1. Sample Size Assumptions

Based on feasibility a sample size of 54 patients will be enrolled in this trial in 1:1:1 ratio to one of the three treatment arms allowing a total of 20% early dropout rate. Assuming as large as 30% standard deviation (s.d.) of percentage reduction of p-ERK score from baseline, 15 subjects per treatment arm will be sufficient to ensure that the 95% confidence interval (CI) will be the mean \pm 16.61%. With 15 patients per treatment arm, the study will have > 97% power to detect 80% reduction of p-ERK score from baseline to Week 2 within a treatment group (with standard deviation (STD) =70%, alpha=0.05, two sided paired t-test).

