5.2. Sample Size Sensitivity

The effect of changes in the assumed standard deviation on the precision (i.e., half-width of the 95% CI for percent reduction of p-ERK score from Baseline at Week 2 within a treatment group) is summarized in [Table 1](#).

Table 1 Effects of changes in the assumption of standard deviation

Standard Deviation (%)	Precision (Half-Width of 95% CI of % reduction of pERK score from baseline within a treatment group)
10	5.538
20	11.076
30	16.613
40	22.151
50	27.689

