9.2.8. Change from baseline

Change from baseline will be presented for safety data as described in Section 12.

Change from baseline is calculated as:

- For records occurring after baseline: (visit value) – baseline value.

Percent change from baseline is calculated as:

- For records occurring after baseline: ((change from baseline) / baseline value) * 100

If either the baseline or visit value is missing, the change from baseline and/or percent change from baseline is set to missing as well.

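### SAP 11.2.1 and its change tables summarise the baseline to Week 2 p-ERK change in Arm C only, although the protocol and SAP 11.2 plan it for every arm

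*SAP*

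**What the plan says.** Both documents justify the arm size with the same interval. SAP 5.1 gives the power to "detect 80% reduction of p-ERK score from baseline to Week 2 within a treatment group", and Protocol 9.2.1 says the same. SAP 5.2 and Protocol 9.2.2 tabulate the "half-width of the 95% CI for percent reduction of p-ERK score from Baseline at Week 2 within a treatment group" (the protocol's wording is nearly identical). Protocol 9.3.5 then says that the percentage reduction from baseline to Week 2 is calculated within a treatment group.

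Protocol 9.3.5.1 and SAP 11.2 add a second interval. In SAP 11.2, "changes in biomarker between screening and week 2 as well as between week 8 and week 10 will be summarized and listed". No arm is excluded, and the section ends: "Summary statistics, graphics, and statistical modeling will be conducted on the biomarker population for each arm of the study".

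SAP 11.2.1 is narrower. It gives scores at each time point for all arms, but actual and percent change only "from baseline to two weeks in Arm C and for change from 8-week and 10-week in Arms A and B". The display list in SAP 18.1.5.1 has the same split:

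- Tables 5.0030 and 5.0070 (the latter for V600E patients): Weeks 8 to 10, arms starting on monotherapy.
- Tables 5.0031 and 5.0071 (V600E): Weeks 0 to 2, the arm starting on combination.

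The mixed model (Tables 5.0040 and 5.0080) uses the same time points by arm.

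SAP 11.2 also words the endpoint in a second way: "The primary endpoint analysis will be the evaluation of the percentage change of the mean" p-ERK H-Score from baseline.

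**The concern.** One SAP gives two instructions for its primary endpoint. A programmer who works from 11.2.1 and the display list will produce no group summary of change from baseline for Arms A and B. Week 8 is not baseline: SAP 9.2.7 sets tumour baseline at Day 1.

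The primary objective concerns monotherapy before combination as well as upfront combination. The Week 2 biopsy in Arms A and B is the early reading of what each drug does alone. If it is shown only as separate score distributions at two visits, the report lacks the figure the protocol promised for those arms. Protocol 9.3.5 requires deviations from its analysis plan to be documented in the RAP, and SAP 11.2.1 records none.

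**Working it through.** **1. The plan's own figures.** Inputs from SAP 5.1 and Protocol 9.2.1: n = 15 per arm, SD of percentage reduction 30%, two-sided 95% interval.

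Half-width = t(0.975, 14) × SD / √n = 2.145 × 30 / √15 = 16.61 points, as stated. For SDs of 10, 20, 30, 40 and 50 the formula gives 5.538, 11.076, 16.613, 22.151 and 27.689, which matches every row of SAP Table 1 and Protocol Table 23. For the power statement (80% reduction, SD 70%, paired t-test), the noncentrality is (80/70) × √15 = 4.43 on 14 df. Power is 98.4%, consistent with the stated figure of more than 97%. The arithmetic is sound, and it describes the SD of individual percentage reductions in each arm.

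**2. What each display gives Arms A and B for baseline to Week 2.**

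| Display | Content | Mean or SD of within-patient change? |
|---|---|---|
| 5.0020, 5.0021 (V600E: 5.0060, 5.0061) | Scores at screening and at Week 2 | No |
| 5.0030, 5.0070 | Change, Weeks 8 to 10 | Different interval |
| 5.0031, 5.0071 | Change, Weeks 0 to 2 | Arm C only |
| 5.0040, 5.0080 | Mixed model, Week 8 against Week 10 for A and B | Different interval |
| 5.0100, Figure 15.0030 | Change after two weeks of combination | Different interval when combination starts on schedule |
| 5.0120 | Response by category of percentage change | No. SAP 11.2.2.1 gives baseline as the start; the end visit is not stated |
| Figures 15.0010 to 15.0021 | Mean and median scores over time | No |
| Listing 25.0010 | Each patient's percent change from baseline | Listed, not summarised |

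**3. Whether the visit tables can stand in.** They cannot supply the SD. SD of change = √[2 × s² × (1 − ρ)] when both visits have SD s. Take s = 49 H-Score points purely as an assumption (it is a mock-up value in the HScore2 shell). Then ρ = 0 gives 69.3 and ρ = 0.8 gives 31.0, with half-widths at n = 15 of 38.4 and 17.2 points. The visit tables do not report ρ.

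They cannot supply the mean percent change either. Take invented baselines of 50, 150 and 280 with Week 2 scores of 50, 30 and 28:

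- Individual changes are 0%, −80% and −90%, with mean −56.7%.
- The means are 160 and 36, so the change of the means is (36 − 160)/160 = −77.5%.

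The two visit tables may also cover different patients, because the Biomarker Population needs a screening biopsy and only one on-treatment biopsy.

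**4. Size.** Two of three arms: 2 × 15 = 30 of 3 × 15 = 45 planned evaluable patients. If 20% of 54 drop out, 54 × 0.8 = 43.2 remain, of whom 28.8 are in Arms A and B.

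**The case against.** The strongest reply is that 11.2.1 is deliberate. It reports the two weeks after combination starts in every arm: Weeks 0 to 2 in Arm C and Weeks 8 to 10 in Arms A and B. That fits the Week 9 rationale in SAP 11.2, and Protocol 9.3.5.1 leaves further detail to the RAP. It explains why the second interval is useful. It does not explain dropping the first. The other stated reason is that biomarker change is most prominent within two weeks of starting treatment, and all three arms start treatment at the outset. Protocol 9.3.5 is also explicit about baseline to Week 2.

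A second reply is that SAP 11.2 defines the endpoint as a change of the mean, which can be worked out for every arm from Tables 5.0020 and 5.0021. That is true of that wording, so the gap depends on reading the endpoint as within-patient. The SD of percentage reduction and the paired t-test in SAP 5.1 support the within-patient reading. A reader might also cite the per-record formula in SAP 9.2.8, "change from baseline) / baseline value) * 100", but that section is introduced for safety data and is weak authority for p-ERK.

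Third, the calculation is still prespecified in Protocol 9.3.5 and SAP 11.2, and the individual values are in Listing 25.0010. This stands, and it limits the severity.

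**Conclusion.** The inconsistency is real and should be fixed. As listed, Arms A and B have no mean or SD of within-patient p-ERK change from baseline to Week 2. This rests on the within-patient reading of the endpoint and on the display list being followed as written.

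Several stronger conclusions might be inferred, and the documents do not support them:

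- **Loss of power or error control.** No hypothesis test or treatment comparison is planned, so the power figure measures no loss.
- **That this quantity set the sample size.** Both documents say 54 was based on feasibility. The half-width and power describe what 15 per arm would give.
- **That Arms A and B alone lose the planned 95% interval.** The HScore3 shell has no CI row for any arm, so that is a separate omission affecting all three.
- **Lost data.** Day 1 and Week 2 tumour biopsies are scheduled in every arm and the individual changes are listed.
- **Dilution from early switching to combination.** The number of patients who switch early is not given, so no effect can be claimed.

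**What to change.** Main change:

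- Amend SAP 11.2.1 to name the same intervals and arms as SAP 11.2 and Protocol 9.3.5.
- Widen Tables 5.0031 and 5.0071 to all three arms, with actual and percent change in H-Score from Day 1 to Week 2 in patients who have both biopsies.
- Keep Weeks 8 to 10 in Arms A and B (Tables 5.0030 and 5.0070, and the mixed model) as an additional summary.
- State in SAP 11.2 that the primary percent change is within-patient rather than a change of the mean.

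Separately, for all three arms, add n and the 95% CI of mean percent change to the HScore3 shell, since the stated precision is that interval.

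A minor separate note: Arm A and B patients who progress on monotherapy may move to combination before Week 8. Flag the treatment being taken at the Week 8 and Week 10 biopsies so that the HScore4 display does not label those patients as on monotherapy.

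The cost is SAP wording, two tables widened from one arm to three, n and CI added to one shell, and one flag. No new biopsies and no protocol amendment are needed.
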